3.3 Rationale for Dose and Escalation Timing

3.3.1 Rationale for Dose Escalation in Part A (Initial Therapy)

Considering the potential for immunogenicity with a protein product, evaluation of the safety and tolerability following multiple rather than single doses prior to escalation is important. Most clinical observations in nonclinical studies occurred by the fourth dose (see Section 1.3). Therefore, In Part A, the decision to escalate into the next dosing cohort (from Cohort 1 to Cohort 2 and from Cohort 2 to Cohort 3) will be made by the Sponsor, based on SRC recommendations after review of safety data from the first subject who completes the first 4 QOW doses in the dose cohort and 24-hour safety data from Subject 3 in the same dose cohort. Intra-patient dose escalation is not planned for Part A.

3.3.2 Rationale for Intra-Patient Dose Escalation in Part B (Therapy at 1 and/or 3 mg/kg)

Based on the experience with neurodegenerative diseases, it is anticipated that clinical response to treatment may not be observed sooner than 6 months after initiating treatment with SBC-103. Therefore, evaluation of safety and tolerability data as well as biomarker and response to treatment data will take place after 24 weeks of treatment in Part A. With the intent of treating patients with the lowest dose that is safe and tolerable and which has potential for efficacy, dose escalation may be proposed for individual subject(s) at any time in Part B as described in Section 3.1.2 and Section 6.1.

3.3.3 Rationale for Additional Dose Escalation in Part C (Therapy at 5 and/or 10 mg/kg)

Preliminary available clinical safety, PK, and PD data (see Section 1.4.1) from this study together with existing toxicokinetic and toxicology data from the juvenile Cynomolgus monkey study provide a safety margin (see Section 1.5.1.4) that supports dose escalation to 5 and 10 mg/kg in Part C. Given the available safety data from Parts A and B and the prior SBC-103 exposure in these patients, 24-hour safety data from 1 subject at each dose are considered appropriate to permit the expansion of each dose cohort, and data from 1 subject who completes the first 2 doses at 5 mg/kg is considered appropriate to initiate dosing at 10 mg/kg.

In addition, ongoing safety and PD data from Part C will be reviewed on an ongoing basis to guide further dose selection (ie, escalation from 5 to 10 mg/kg or reduction from 10 to 5 mg/kg) in this study with the goal of treating patients at the lowest dose that is likely to demonstrate clinical benefit while also being safe and tolerable.

3.4 Study Endpoints

3.4.1 Primary Endpoint

The primary endpoint of this study is safety and tolerability of SBC-103 in subjects with MPS IIIB. The safety assessments will include the following:

- Incidence of AEs, SAEs, and IARs;
- Changes from baseline in clinical laboratory tests (hematology, serum chemistry, and urinalysis) and CSF findings (cell counts, glucose, and protein);
- Changes from baseline in 12-lead electrocardiograms (ECGs);
- Changes in vital signs during and post-infusion, relative to pre-infusion values;
- Physical examination findings;
- Use of concomitant medications/therapies;
- Assessment of ADAs, including seroconversion rate, time to seroconversion, and ADA titer by time point, peak ADA titer, and ADA titer status (positive/negative), and the effect of ADAs on the safety of SBC-103, including the relationship between ADA-positive subjects and the incidence of IARs.

3.4.2 Secondary Endpoints

The secondary endpoints of this study are baseline and post-treatment measures of the following assessments:

- PK profile of SBC-103 after single and multiple doses:
 - Maximum observed serum concentration (C_{max})
 - Time to reach $C_{max}(T_{max})$
 - Area under the concentration-time-curve from time 0 to the last measurable time point (AUC_{last})
 - Area under the concentration-time-curve extrapolated to infinity (AUC_{∞})
 - Half-life $(T_{1/2})$

- Clearance (CL)
- Volume of distribution at terminal phase (V_z)
- Accumulation ratio (R_{ac})
- Effects of SBC-103 treatment on the onset, magnitude, and reversibility of changes in levels of total HS in CSF, serum, and urine.
- Neurocognitive and developmental function as determined by the scores on Vineland Adaptive Behavior Scales, Second Edition (Vineland-II) and, as appropriate to the subject's age, the Bayley Scales of Infant and Toddler Development, Third Edition (BSID-III) or Kaufman Assessment Battery for Children, Second Edition (KABC-II), Bruininks-Oseretsky Test of Motor Proficiency, Second Edition, Brief Form (BOT-2 Brief Form), and Children's Communication Checklist, Second Edition (CCC-2).
- Brain structure as determined by the relative proportion of grey and white matter volume and indices of microstructural integrity as assessed by MRI of the brain.
- Effect of temporary interruption of SBC-103 therapy (between Parts A and B) on safety, tolerability, and select PD/efficacy markers.

3.4.3 Exploratory Endpoints

Exploratory endpoints in this study include measures to examine the onset, magnitude, and reversibility of changes in exploratory biomarkers, SBC-103 concentration in CSF, MPS IIIB disease characteristics, symptoms, and QOL after IV administration of SBC-103:

- Biomarkers:
 - Change in non-reducing end (NRE) HS derivatives in CSF, serum, and urine
 - Changes in serum ferritin and chitotriosidase
 - Changes in CSF-disease related biomarkers including but not limited to, hepatocyte growth factor (HGF), calbindin D, Tau, pTau, amyloid β, albumin, IgG, glutamic acid, and glycine
 - Changes in glutamic acid and glycine in relation to plasma (carrier-mediated excitatory amino acids that are markers of transport function)
 - Changes in CSF/serum albumin index (CSF-AI).
 - Changes in IgG index ([CSF/serum IgG ratio] / [CSF-AI])
 - Changes in inflammatory markers in serum
- Disease characteristics, symptoms, and QOL
 - Assessment of sleep disorders or dysfunction as determined by the Children's Sleep Habits Questionnaire (CSHQ)
 - Assessment of behavior as determined by the Sanfilippo Behavior Rating Scale (SBRS)
 - Assessment of subjective QOL as determined by the Short Form Health Survey for Children (SF-10)
 - Assessment of caregiver QOL as determined by the Zarit Burden Interview (ZBI) 12-item short form

- Coarsening of features by Facial Dysmorphology Novel Analysis (FDNA)
- Additional blood or urine biomarkers of interest that are identified during the course of this study based on emerging data from the scientific literature or the Sponsor's MPS IIIB development program (if there is sufficient sample volume and if local regulations permit).
- Assessment of genes that may contribute to and/or modify the disease phenotype via a DNA sample (where local regulations permit and subject to discretionary approval from each center's Institutional Review Board [IRB]/Independent Ethics Committee [IEC] and the consent/assent of the subject [and/or consent of the subject's parent or legal guardian]).

4 STUDY POPULATION

4.1 Target Population

The target population for this study is male and female subjects with documented MPS IIIB who are greater than or equal to 2 years old but less than 12 years old.

4.2 Number of Subjects

Approximately 9 subjects with MPS IIIB are planned to be treated in this study. All subjects may enter Part B if they meet eligibility criteria described in Section 4.3.3, and once the site has received approval to escalate to doses of 5 and 10 mg/kg, subjects may enter Part C if they meet eligibility criteria described in Section 4.3.4.

4.3 Eligibility Criteria

4.3.1 Inclusion Criteria

A subject who meets all of the following inclusion criteria will be eligible to participate in this study:

- 1. Has a definitive diagnosis of MPS IIIB, as determined by either of the following:
 - a. Documented deficiency in NAGLU enzyme activity $\leq 10\%$ of the mean value in normal individuals (Heron, 2011, *Am J Med Genet A*) based on test results from a central laboratory at Screening.

OR

- b. Documented functionally-relevant mutations in both alleles of the NAGLU gene based on historical test results from a local laboratory (if available) or results from the central laboratory at Screening.
- 1. Greater than or equal to 2 years old and less than 12 years old at the time of written informed consent, and has an age equivalent of ≥ 1 year on the Vineland-II.
- 2. Has documented developmental delay with onset before 6 years of age, as defined by:
 - a. Cognitive delay evaluated by BSID-III or KABC-II.

OR

- b. Language delay, plateauing or regression of language skills as determined by the Investigator and confirmed by the Vineland-II (communication domain) administered at Screening (eg, subject uses isolated words, associated words such as two-word combination, sentences, poor or reduced language and/or language difficult to understand).
- 3. Subject or subject's parent or legal guardian (if applicable) consents to participate in the study and provides informed consent prior to any study procedures being performed. If the subject is of minor age; he/she is willing to provide assent where required per local regulations, and if deemed able to do so.
- 4. Female subjects who are of childbearing potential at the time of consent or who become of childbearing potential during participation on study (a) must have a negative urine pregnancy test at Screening, (b) cannot be breast feeding, and (c) must consent to use a highly reliable method of birth control (expected failure rate less than 5% per year) for the duration of the

study and for 30 days after last dose of SBC-103. Women may be considered of non-childbearing potential if they have not started their menses or are surgically sterile (ie, total hysterectomy or bilateral salpingo-oophorectomy).

- 5. Male subjects must consent to use a highly reliable method of birth control (expected failure rate less than 5% per year) during any sexual contact with females of childbearing potential while participating in the study and for 30 days following discontinuation from this study even if he has undergone a successful vasectomy.
- 6. Willingness and ability to comply with protocol requirements to the extent that may be expected of a subject with cognitive impairment.

4.3.2 Exclusion Criteria

A subject who meets any of the following exclusion criteria will be ineligible to participate in this study:

- 1. Received treatment with gene therapy at any time, or any investigational drug (including high dose genistein > 150 mg/kg/day), or device intended as a treatment for MPS IIIB within 30 days prior to Screening, or is currently being treated in another study that involves an investigational drug or device.
- 2. Has any internal or non-removable external metal items that may present a safety risk for study assessments that utilize magnetic fields, or any other medical condition or circumstance in which an MRI is contraindicated according to local institutional policy.
- 3. Previous hematopoietic stem cell or bone marrow transplant.
- 4. Known or suspected hypersensitivity to anesthesia or the use of a sedative is contraindicated for any other reason.
- 5. History of poorly controlled seizure disorder.
- 6. A bleeding disorder, or any other medical condition or circumstance in which a lumbar puncture (for collection of CSF) is contraindicated according to local institutional policy.
- 7. Known hypersensitivity to eggs. Subjects at high risk for food allergy that may include eggs should be tested according to local guidelines.
- 8. Other medical conditions or co-morbidities (eg, ALT or AST > 3x ULN, confirmed by repeat testing, analyzed centrally or locally and based on the standardized reference range provided in the central laboratory manual), or other markers of clinically significant liver dysfunction (eg, elevated bilirubin, [with the exception of patients with confirmed Gilberts Disease] confirmed by repeat testing, or elevated prothrombin time [PT]/International normalized ratio [INR] confirmed by repeat testing analyzed centrally or locally and based on the standardized reference range provided in the central laboratory manual) which in the opinion of the Investigator, in consultation with the Sponsor, would interfere with study compliance, or confound data interpretation.

4.3.3 Qualifications for Participation in Part B (Therapy at 1 and/or 3 mg/kg)

Subjects are eligible for continued SBC-103 dosing in Part B if they do not meet any Exclusion criteria listed above and if they meet the following:

- 1. Completion of Part A with no unmanageable study drug toxicity;
- 2. Continue to meet Section 4.3.1 Inclusion Criteria items 4-7; and

3. SRC and Sponsor have reviewed the subject's safety data from Part A and have deemed it acceptable for the subject to re-initiate dosing in Part B.

4.3.4 Qualifications for Participation in Part C (Therapy at 5 and/or 10 mg/kg)

Subjects are eligible for continued SBC-103 dosing at a higher dose (5 or 10 mg/kg QOW) in Part C if they do not meet any Exclusion criteria listed above and if they:

- 1. Have completed at least 4 doses of 3 mg/kg in either Part A or Part B with no unmanageable study drug toxicity; and
- 2. Continue to meet Section 4.3.1 Inclusion Criteria items 4-7.

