5.2 Clinical Laboratory Assessments

5.2.1 Routine Assessments and Biomarkers

A list of all clinical laboratory tests that will be performed is provided in Table 4; the time points for sample collection are specified in the SOA. Central lab reference ranges will be used throughout the study, including in the event that labs are analyzed locally. All attempts should be made to draw lab samples for central lab analysis when samples are needed for local analysis.

Blood will be collected for standard hematology and serum chemistry (including coagulation parameters).

During Screening, if a subject's ALT or AST is greater than $3 \times ULN$; or a subject has elevated bilirubin or PT/INR, confirmatory testing will be completed. Confirmatory testing may be completed locally or by the central lab, however results will be based on the standardized reference ranges provided in the central laboratory manual for this study. Abnormal safety labs at Screening can be repeated within 1 to 2 weeks. The difference between these two pre-treatment values for each abnormal lab should differ by <20% in each subject.

Efforts should be made by the Investigator to review subject medical history, concomitant medications and health status so that a clear explanation for the elevation is established. The Investigator, in consultation with the Sponsor, shall make a determination of subject eligibility based on review of Exclusion Criteria #8.

During the study, after treatment with SBC-103, in the event that a subject's ALT or AST are $2 \times$ ULN (when baseline ALT or AST were within normal limits) or $3 \times$ ULN (when baseline ALT or AST was greater than $1.5 \times$ ULN), or when a subject has an elevation in bilirubin or PT/INR a confirmatory test should be completed at the earliest possible time point, but not later than the next scheduled visit. Upon positive confirmation of the elevated transaminases as described above, dosing will be paused until AST and ALT have returned to baseline or to study nadir (nadir values may be confirmed by additional lab sampling at the discretion of the investigator, using the same lab for analysis of each sample), or normalized if the baseline level was within normal limits. See Section 6.2.1 for stopping rules.

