Due to the limitations on the volume of blood collection that is considered to be acceptable in young children with very small total circulating blood volumes; see Committee for Medicinal Products for Human Use (CHMP) and Pediatric Committee (PDCO) guidance (EMEA/536810/2008, adopted 25 June 2009), the blood laboratory tests will be ranked by tier. Per individual, the study-related blood loss should not exceed 3% of the total blood volume during a period of four weeks and should not exceed 1% at any single time. The total volume of blood is estimated at 80 to 90 mL/kg body weight; 3% corresponds to about 2.4 to 2.7 mL blood per kg body weight.

Only Tier 1 assessments (see Table 4) are considered mandatory and all efforts should be made to collect these samples in all subjects. Samples for the Tier 2 or Tier 3 assessments will be collected if permitted based on the blood or CSF volume threshold for a subject's weight, as well as the subject's clinical status.

All tests will be performed by a central laboratory with the exception of the urine pregnancy test (or serum pregnancy test if the urine cannot be collected), CSF routine findings, and (as of 23 March 2015) all coagulation panels, which will be done locally.

Clinical laboratory samples will be stored by the Sponsor or designee in a secure and controlled environment until analysis, and will be destroyed by the Sponsor or designee after all worldwide obligations have been met, or sooner if required by local regulations.

Refer to the laboratory manual for further details regarding the collection, processing, and storage of clinical laboratory samples.

Page 67 of 121

Lab Panel	Tier	Matrix	Tests		
Hematology	1	Whole Blood	White blood cell count; red blood cell count; hemoglobin; hematocrit; MCV, MCH, MCHC; platelet count; neutrophil; lymphocytes; monocytes; eosinophils; basophils;		
Serum Chemistry	1	Serum	ALT, AST, alkaline phosphatase, GGT, albumin, total bilirubin, serum electrolytes (sodium, potassium, chloride, calcium, magnesium, phosphorus), glucose, creatinine, bicarbonate, total protein, BUN		
Coagulation	1	Plasma ^c	PT, INR ^c		
Urinalysis	N/A	Urine	pH, clarity, color, specific gravity, glucose, ketones, blood, protein, nitrite, and leukocytes (microscopic examination will only be done if urinalysis is positive for blood, nitrite, or leukocytes, or if protein is $>1+$)		
Pregnancy test ^a	N/A	Urine			
MPS IIIB	1	Dried blood spot	NAGLU enzyme activity		

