- 11. All AEs should be followed until they have returned to baseline values or stabilized or until the Investigator and Sponsor or designee agree that follow-up is no longer necessary.
- 12. Information on all medications and treatments received by the subject within the 4 weeks preceding the Screening visit through the final visit will be recorded in the CRF.

14.4 Appendix D: Schedule of Study Assessments (Part C, Therapy at 5 and/or 10 mg/kg)

Schedule of Study Assessments															
Part C: Therapy at 5 and/or 10 mg/kg (Weeks 1 through 26)															
Assessments	Wk 1C D0C	Wk 1C D1C*	Wk 2C	Wk 4C	Wk 6C	Wk 8C	Wk 10C	Wk 12C	Wk 14C	Wk 16C	Wk 18C	Wk 20C	Wk 22C	Wk 24C	Wk 26C
Visit Window (Days)**	±5		±5	±5	±5	±5	±5	±5	±5	±5	±5	±5	±5	±5	±5
Part C Informed Consent/Assent	X ^P														
Part C Eligibility Assessment	X ^P														
Physical Examination	X ^P	Х		X ^P		X ^P		X ^P		X ^P		X ^P		X ^P	
Height and Weight	X ^P			X ^P		X ^P		X ^P		X ^P		X ^P		X ^P	
Vital Signs ¹	Х	 										Х			
12-lead ECG	X ^P	X ^p X ^p X ^p X ^p													
FDNA	Х	X X X													
Vineland-II, BSID-III, KABC-II, BOT-2 BF, CSHQ, CCC-2, SBRS, ZBI 12-item, SF-10 ^{2,3}	X ^{P,3} X														
Hematology, Serum Chemistry (including Coagulation ⁴), Urinalysis ⁵	X ^P	X^{P} X X^{P} X^{P} X^{P} X^{P} X^{P} X^{P} X^{P}													
Pregnancy Test (Urine) ⁶	X ^P			X ^P		X ^P		X ^P		X ^P		X ^P		X ^P	
Serum and Urine Heparan Sulfate (Total and NRE)	X ^P			X ^P		X ^P		X ^P		X ^P		X ^P		X ^P	
Serum Ferritin and Chitotriosidase	X ^P X ^P X ^P X ^P X ^P X ^P							X ^P							
Plasma Glutamic Acid and Glycine	X ^P			X ^P		X ^P		X ^P		X ^P		X ^P		X ^P	
Exploratory Serum Biomarkers including IgG and Inflammatory Markers	X ^P			X ^P		X ^P		X ^P		X ^P		X ^P		X^{P}	
Serum Pharmacokinetic Profile ⁷	Х							Х						Х	
SBC-103 ADA ⁸	X ^P			X ^P		X ^P		X ^P		X ^P		X ^P		X ^P	
General Anesthesia/Sedation ⁹	X ^P							X ^P						X ^P	
Lumbar Puncture ^{4,9,10,11}	X ^{P,11}							X ^P						X^{P}	
Heparan Sulfate (Total and NRE) in CSF	X ^{P,11}							X ^P						X ^P	
Calbindin D, HGF, Tau, pTau, Amyloid β , Albumin, IgG in CSF	X ^{P,11}							X ^P						X^{P}	
Glutamic Acids and Glycine in CSF	X ^{P,11}							X ^P						X ^P	
Routine Findings in CSF (Cell Counts, Glucose, Protein)	X ^{P,11}							X ^P						\mathbf{X}^{P}	
SBC-103 in CSF	X ^{P,11}							X ^P						X ^P	
Structural and Diffusion MRI ^{9,12}	X ^{P,12}													X ^P	
SBC-103 Dosing	Х		Х	Х	Х	Х	Х	Х	Х	Х	Х	Х	Х	Х	Х

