Adverse Events ¹³	CONTINUOUS														

Page 111 of 121

	Schedule of Study Assessments															
		Pa	rt C: The	apy at 5 a	nd/or 10	mg/kg (Weeks 1	through	26)							
Assessments	Wk 2C	Wk 4C	Wk 6C	Wk 8C	Wk 10C	Wk 12C	Wk 14C	Wk 16C	Wk 18C	Wk 20C	Wk 22C	Wk 24C	Wk 26C			
1 135C55IIICIIIC5		DUC	DIC	-		00	00	100	120	110	100	100	100		10	100
	Visit Window (Days)**	±5		±5	±5	±5	±5	±5	±5	±5	±5	±5	±5	±5	±5	±5
Concomitant Medications ¹⁴		CONTINUOUS														

* The Week 1C Day 1C visit applies only to the first subject at each dose level.

** All study visits will be scheduled relative to Week 1 Day 0 in Part C; infusions must be administered at least 10 days apart.

X^P Assessments to be performed pre-dose.

1. Starting at Week 26C, vital signs will be taken pre-dose (within approximately 30 minutes), approximately every 15 minutes during infusion and approximately every 15 minutes for 1 hour after completion of the infusion, provided there is no occurrence of IARs during the infusion. Vital signs will be obtained after any lumbar puncture as per site standard of care.

- 2. The Vineland-II, BSID-III or KABC-II, BOT-2 Brief Form, and CCC-2 should be administered in-person by an appropriately qualified professional; where possible, the test should be administered prior to dosing.
- 3. Neurocognition testing performed within 8 weeks prior to Day 0 in Part C may be used as the Day 0C baseline in lieu of repeating the assessments on Day 0C.
- 4. The coagulation laboratory panel should be collected within 48 hours prior to performing the lumbar puncture, and the results should be available prior to sedating/anesthetizing the subject or performing the lumbar puncture. The procedure (including the initiation of sedation/anesthesia) will not commence until the site receives these results and confirms that it is safe for the subject to receive anesthesia/sedation and the lumbar puncture. To facilitate this process, all coagulation panels (as of 23 March 2015) will be drawn and analyzed locally rather than sent to the central laboratory for analysis.
- 5. Central lab reference ranges will be used throughout the study, including in the event that labs are analyzed locally. All attempts should be made to draw lab samples for central lab analysis when samples are needed for local analysis.
- 6. If a urine sample is not able to be provided, a serum pregnancy test will be performed by a local laboratory.

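### Part C re-applies the liver exclusion, but nothing requires ALT, AST or bilirubin to be reviewed before the first 5 or 10 mg/kg infusion, and the last earlier scheduled result can be 42 to 56 days old

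*Protocol*

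**What the plan says.** Section 4.3.4 admits children to higher dosing "in Part C if they do not meet any Exclusion criteria listed above", provided they have completed at least four doses of 3 mg/kg without unmanageable toxicity and still meet inclusion items 4 to 7. The re-applied exclusions include item 8 of Section 4.3.2. Its liver examples are "ALT or AST > 3x ULN, confirmed by repeat testing", elevated bilirubin and elevated PT/INR. They count when the Investigator, consulting the Sponsor, thinks they would interfere with compliance or confound the data.

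Appendix D schedules "Part C Informed Consent/Assent", "Part C Eligibility Assessment", the serum chemistry draw and the first Part C infusion all at Wk 1C D0C. The first three carry the pre-dose mark, which the key defines only as "Assessments to be performed pre-dose". It does not say that results must be seen. Section 5.2.1 states that "All tests will be performed by a central laboratory with the exception of the urine pregnancy test" and a few other items, among them coagulation. Chemistry is therefore central by default, although the same section contemplates local analysis read against central reference ranges.

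The on-treatment liver rule in Section 5.2.1 acts after confirmation: "Upon positive confirmation of the elevated transaminases as described above, dosing will be paused". The repeat is due as early as possible but "not later than the next scheduled visit".

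Entry to the lower doses is spaced differently. Part A uses Screening chemistry inside a 28-day window. Part B places its eligibility assessment at Week 26, between the Week 24 chemistry and the Week 28 dose. Section 4.3.3 item 3 also requires the SRC and Sponsor to have reviewed that child's safety data. Section 4.3.4 has no matching item.

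**The concern.** An exclusion that depends on laboratory values works only if recent values are seen before the decision. A site that follows Appendix D exactly can judge exclusion 8 on whatever chemistry is on file, draw the D0C sample, infuse 5 or 10 mg/kg, and learn the D0C result afterwards.

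What could be missed is a new transaminase or bilirubin rise since the last Part B draw. Under Section 6.2.1 a confirmed ALT/AST rise leads to a pause and a restart at a lower dose. Here the dose could go up first. After the first child at each dose level, the others may be dosed in parallel (Section 3.1.3.1). The Day 1C visit, with its chemistry, applies only to those first two children. For the other 9 of 11, the next scheduled chemistry after D0C is at Week 4C.

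**Working it through.** The documents state no look-back figure to reproduce. The check is calendar arithmetic on nominal visit days.

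**Inputs**
- Part B chemistry visits (Appendices B and C): Weeks 28, 36, 44, 52, 60, 68, 78.
- Time in Part C (SAP Section 4): 90 to 110 weeks, ending at Week 156. Entry is then from 156 − 110 = Week 46 to 156 − 90 = Week 66, which gives 11 two-weekly visits.
- SAP Section 9.4.1: for some children the Week 52 visit was the Part C baseline visit.
- Part B lumbar punctures in range: Weeks 40, 52, 66. One done within 4 weeks before D0C may replace the D0C puncture (Section 3.1.3).
- Lumbar punctures require a coagulation sample within 48 hours, with results in hand (Section 5.2.1.4).

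**Formula.** Age in days = 7 × (entry week − latest scheduled chemistry week before entry). Draws are pre-dose, so the infusion on the draw day counts among those given since.

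| Entry week | Last earlier chemistry | Age (days) | Infusions since | Lumbar puncture due at D0C |
|---|---|---|---|---|
| 46 | 44 | 14 | 1 | yes |
| 48 | 44 | 28 | 2 | yes |
| 50 | 44 | 42 | 3 | yes |
| 52 | 44 | 56 | 4 | yes |
| 54 | 52 | 14 | 1 | can be waived |
| 56 | 52 | 28 | 2 | can be waived |
| 58 | 52 | 42 | 3 | yes |
| 60 | 52 | 56 | 4 | yes |
| 62 | 60 | 14 | 1 | yes |
| 64 | 60 | 28 | 2 | yes |
| 66 | 60 | 42 | 3 | yes |

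At Week 52 the scheduled Week 52 draw is itself the D0C draw, so the last earlier one is Week 44.

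**Results**
- 14 to 28 days at 6 of 11 entry weeks; 42 days at Weeks 50, 58 and 66; 56 days at Weeks 52 and 60. The median over the 11 weeks is 28 days.
- With ±5-day windows at both visits, the Week 52 figure runs from 56 − 10 = 46 to 56 + 10 = 66 days.
- Part A: at most 28 days. Part B: the Week 24 draw precedes a first dose given 4 weeks to 4 weeks and 3 days later, so 28 to 31 days with one infusion since.
- A lumbar puncture is due at D0C at 9 of 11 entry weeks, including all 5 above 31 days. A results-in-hand local coagulation draw is therefore already required at each of those 5.

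**The case against.** The other side has real substance.

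- Section 5.1.2 requires eligibility to be complete before Day 0 procedures, with Sponsor agreement, and Section 5.1 applies its assessments to all three parts unless stated otherwise. A reader might infer that Part C has no eligibility check. That is wrong: there is one, and it is marked pre-dose. But Section 5.1.2 names neither Day 0C nor the infusion nor laboratory results, and sets no age limit on a result.
- Exclusion 8 is a judgement, not a fixed liver cutoff, and PT/INR is one of its markers. Where a lumbar puncture is due, PT/INR is already in hand. ALT, AST and bilirubin are not.
- The Section 6.2.1 pause rules run throughout Part B, and for a child with normal baseline they act at 2x ULN, below exclusion 8's 3x. Only a rise since the last draw can go unseen. This stands and limits the size of the point.
- Escalation within Part B may happen at any time with no laboratory look-back, and Section 3.3.3 justifies Part C by prior exposure and existing safety data. Reliance on routine monitoring is thus consistent. However, Section 4.3.4 itself re-applies the exclusions at this step, and a criterion that is re-applied should be checkable.
- Central turnaround is unknown and the laboratory manual is not available. If results return the same day, all that remains is that review before dosing is not stated.
- A results check alone would not stop the infusion, because exclusion 8's transaminase example and the pause both need confirmation. Holding on one unconfirmed value is a new rule and should be presented as such.

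**Conclusion.** The gap is real and modest. Part C re-applies a liver-related exclusion on a schedule that allows the first escalated infusion before current ALT, AST and bilirubin are reviewed. If D0C central results are not available the same day, the last earlier scheduled chemistry is 42 to 56 days old at 5 of the 11 SAP-implied entry weeks, one of which (Week 52) the SAP says occurred. It is no older than 28 days at the other 6. About one infusion per child is at issue.

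The count is over possible entry weeks on nominal days, not over children; the documents do not give each child's entry week.

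Three stronger readings are not supported:
- **That results are typically 6 to 8 weeks old at entry.** The median over entry weeks is 28 days.
- **That the Part C baseline or attribution of later changes is compromised.** The D0C sample is pre-dose and remains the baseline under SAP Section 9.4.1.
- **That children were escalated with no chemistry after any 3 mg/kg dose.** This is possible only if the first 3 mg/kg dose fell at Week 44 with entry at Week 52, or at Week 52 with entry at Week 60. It could concern at most 11 − 4 (Cohort 3) − 2 (Cohort 2 children already on 3 mg/kg, Section 1.4.1) = 5 children. Nothing shows that it happened.

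**What to change.** Add to Section 4.3.4, and as an Appendix D footnote at D0C:

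1. The Investigator must review ALT, AST and bilirubin before the first Part C infusion. The results may come from a draw within 3 days before D0C, which then replaces the D0C draw (Appendix A footnote 8 already allows this for Part A), with Part C consent taken by that draw. Alternatively, they may come from local analysis alongside the pre-lumbar-puncture coagulation sample, read against central reference ranges.
2. If a value is above the exclusion 8 level (ALT/AST >3x ULN, or elevated bilirubin) or at the Section 6.2.1 pause level, escalation is deferred only until the confirmatory repeat is available. Meanwhile the child may continue the current 3 mg/kg dose under the existing Section 6.2.1 rules, and stays eligible if the value is not confirmed.
3. State openly that this is a one-time hold before escalation, added to the confirmed-elevation rule. Dose levels and the Section 6.2.1 thresholds for pausing treatment do not change.

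The cost is one footnote and two or three sentences. The local route needs one small extra tube in a draw already required at 9 of the 11 entry weeks. The early route moves a draw and consent up to 3 days forward. The downside is an occasional short delay to escalation for a child whose raised value is not confirmed.
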